### 9.3.4 Handling of Repeated Laboratory Test Results

Repeated laboratory test data will be handled after identifying the reason. If it is due to a test error, then the last value of the visit will be used, and if a clinical opinion is required, then the team will request the clinician's opinion and will decide what value to use.

### 9.4 Handling of Early Termination

In order to analyze and summarize the data consistently, the last visit performed for Early Termination will be mapped to their closest to scheduled visit within the analysis dataset.

For example, if a subject completed efficacy measurement at Week 0, then the subject got early terminated from the study 4 weeks later and completed efficacy measurement, then the efficacy measurement for ET will be mapped to Week 4 visit.

Example #1:

Before:

Week 0 (02FEB2017)	ET (02MAR2017)
Efficacy Measurement – Done	Efficacy Measurement – Done

After:

Week 0 (02FEB2017)	Week 4 (02MAR2017)
Efficacy Measurement – Done	Efficacy Measurement – Done

Note: Week 2 to Week 12 have  $\pm 3$  day visit window

Example #2:

Before:

Week 0 (02FEB2017)	ET (05MAR2017)
Efficacy Measurement – Done	Efficacy Measurement – Done

After:

Week 0 (02FEB2017)	Week 4 (05MAR2017)
Efficacy Measurement – Done	Efficacy Measurement – Done

Note: Week 2 to Week 12 have ± 3 day visit window

For example, if a subject completed efficacy measurement at Weeks 0, 4, 8 then the subject got early terminated from the study 4 weeks later after Week 8 and completed efficacy measurement, and then the efficacy measurement for ET will be mapped to Week 12 visit.

Example #3:

Before:

Week 0 (29MAR2017)	Week 4 (26APR2017)	Week 8 (24MAY2017)	ET (21JUN2017)
Efficacy Measurement – Done	Efficacy Measurement – Done	Efficacy Measurement – Done	Efficacy Measurement – Done

After:

Week 0 (29MAR2017)	Week 4 (26APR2017)	Week 8 (24MAY2017)	Week 12 (21JUN2017)
Efficacy Measurement – Done	Efficacy Measurement – Done	Efficacy Measurement – Done	Efficacy Measurement – Done

Note: Week 2 to Week 12 have ± 3 day visit window

Each case will be discussed and decided with the study team and will be documented in the analysis dataset specification.

### 9.5 Outliers Detection

Histograms or raw data review will be examined to identify outliers in any of the continuous variables used in the analyses. Unexpected and/or unexplained values in categorical data will be identified by utilizing frequency tables.

Outliers due to data entry errors will be corrected by the study team before the database lock. The validity of any questionable values or outliers will be confirmed. Outliers or any questionable values with confirmed validity will be included in the analyses. However, ad-hoc sensitivity analyses may be conducted to evaluate the influence of extreme values in the data. If it is deemed necessary after the team reviews the output from the planned analyses after the database lock, post-hoc analyses excluding subjects with outliers may be performed.

## 9.6 Bias Detection

Randomization and blinding are performed for avoiding bias in this phase 2 study. Major protocol deviations will be listed and or/tabulated in the clinical study report (CSR). Any breaking of the blind for individual subjects prior to unblinding of the study will be documented in the CSR. The timing of and reasons for premature withdrawal from treatment and from study will be tabulated and /or listed.

## 9.7 Distributional Characteristics

Continuous endpoints of change from baseline value will be analyzed under normality assumption. If they deviate appreciably from normality, then appropriate non-parametric alternatives will be considered.

## 9.8 Validation of Statistical Analyses

The procedure for the validation of the analysis result is as follows:

- 1) Self-check: The BSA in charge will check for oneself that the SAS program code, output, execution log, etc. are written correctly.
- 2) Double programming and the review: The BSA in charge and other BSA will write SAS program code independently, and the Bio-statistics manager (BSM; Reviewer) will compare the outputs such as table, graph, listing that are printed by the SAS program code.
- 3) Source code check: The BSM will check the written source code visually, and will check whether it is properly processed according to its purpose.
- 4) Table/Graph: The BSM will check the values displayed in tables and graphs.
- 5) Listing/Raw data: The BSM will check whether the raw data and listing are the same or not.

# 10. STATISTICAL ANALYSES

## 10.1 General Principles

Statistical analysis will be conducted after database is locked and performed using SAS software version 9.4 according to this SAP. If statistical analysis methods are changed, it will be described in the final clinical study report.

Continuous variables will be summarized with means, standard deviations, medians, 25th & 75th percentiles, minimums, and maximums. Categorical variables will be summarized with counts and percentages. P-values less than 0.05 will be considered statistically significant. No adjustments for multiple comparison will be made to the result presented in this study because this is a phase 2 clinical trial and it is not formally powered with statistical algorithms.

## 10.2 Subject Disposition

The disposition of all randomized patients will be tabulated by randomized treatment group. The numbers of all patients classified as follows will be summarized with count, percentage and flow chart by site and treatment group.

- All patients who enrolled into the study
- Patients who were randomized
- Patients who were treated
- Patients who were completed
- Prematurely withdrawn
- The reasons for premature withdrawal

## 10.3 Protocol Deviations

- All protocol deviations occurred during this study will be summarized by treatment group. Subjects who have protocol deviations will be categorized as follows;
  - 1) Subjects who have visits outside window
  - 2) Subjects who have not met inclusion criteria or met exclusion criteria but were entered into the study
  - 3) Subjects who received an excluded concomitant medications/treatment
  - 4) Subjects who have other protocol deviations
- Individual patients with these protocol deviations will be listed by site.

## 10.4 Demographic and Baseline Characteristics

Demographic characteristics, medical history, medication history, extent of exposure, and efficacy variables at baseline will be summarized using descriptive statistics by randomized treatment group and overall study population using FAS and Safety Analysis Set. Continuous variables will be summarized with mean, standard deviation, median, 25th & 75th percentiles, minimum and maximum. Categorical variables will be summarized with count (number of subjects and/or number of events) and percentage. Because, in theory, the goal of randomization is to balance out the subject characteristics, statistical tests are not planned for these variables.

### 10.4.1 Demographic Characteristics

- Sex (Male, Female)
- Age
- Ethnicity (Hispanic, Non-Hispanic)
- Race (Black or African American, Native Hawaiian or other Pacific Islander, Native American Indian or Native Alaskan, Asian, White, Other)
- Height

#### 10.4.2 Medical History

- Type of Diabetes (Type I Diabetes, Type II Diabetes, Gestational Diabetes)
- Diabetes disease period
- Past medical history status (Yes, No) and past medical history classified by System Organ Class (SOC) and Preferred Term (PT) according to MedDRA (Medical Dictionary for Regulatory Activities) version 20.0.
- Present medical history status (Yes, No) and present medical history classified by SOC and PT according to MedDRA version 20.0

#### 10.4.3 Concomitant Medications

- Status (Yes, No) of concomitant medications and concomitant medications classified by Level1 and Level2 according to Anatomical Therapeutic Chemical (ATC) code WHODRUG version 2017 at V1 (screening)

#### 10.4.4 Efficacy Variables at Baseline

- HbA1c
- Body Weight (BW)
- FPG level
- Waist Circumference
- Mean value of postprandial (2 hours after dinner) blood glucose level
- OGTT
- ADDQoL questionnaire scores
- Thyroid Function Test: TSH, T3, and T4
- Serum parameters: zinc, insulin, adiponectin, C-peptide, leptin, and glucagon
- Urine parameters: zinc, glucose, microalbumin, and copper
- TAFGC
- BMI

#### 10.5 Efficacy Analyses

The analyses of efficacy endpoints will utilize EAS. Subjects will be analyzed according to their randomized treatment group regardless of the actual treatment received during the study. Per protocol analyses of the primary, secondary, and exploratory endpoints will utilize the Per Protocol Set.

Detailed primary analysis methods, sensitivity analyses are summarized in the table below.

Endpoints	Primary Analysis and Analysis Method	Sensitivity Analysis at Week 12
Primary Endpoints		
Change of HbA1c level from baseline at Week 12 Change of BW from baseline at Week 12	1. EAS: Summary statistics by visit using observed data 2. EAS: ANOVA model and Dunnett's test, and paired t-test	1. LOCF, EAS : Summary statistics and analyze using an ANOVA model and Dunnett's test, and paired t-test 2. Per Protocol Set : Same as primary summary and analysis method at Week 12
Secondary Endpoints		
Change of FPG level from baseline at Week 12	1. EAS: Summary statistics by visit using observed data 2. EAS: ANOVA model and Dunnett's test, and paired t-test	1. LOCF, EAS : Summary statistics and analyze using an ANOVA model and Dunnett's test, and paired t-test 2. Per Protocol Set : Same as primary summary and analysis method at Week 12
Proportion of subjects achieving HbA1c goal of < 7.0% at Week 12	1. EAS: Summary statistics by visit using observed data 2. EAS: Chi-square test	1. LOCF, EAS : Summary statistics and analyze using chi-square test 2. Per Protocol Set : Same as primary summary and analysis method at Week 12
Proportion of subjects achieving HbA1c goal of < 6.5% at Week 12	Same as above	Same as above
Change in waist circumference from baseline at Week 12	1. EAS: Summary statistics by visit using observed data 2. EAS: ANOVA model and Dunnett's test, and paired t-test	1. LOCF, EAS : Summary statistics and analyze using an ANOVA model and Dunnett's test, and paired t-test 2. Per Protocol Set : Same as primary summary and analysis method at Week 12
Change of postprandial (2 hours after dinner) blood glucose level from baseline at Week 12	Same as above	Same as above
Change of OGTT from baseline at Week 12	Same as above	Same as above
Change of score in ADDQoL questionnaire from baseline at Week 12	Same as above	Same as above

Endpoints	Primary Analysis and Analysis Method	Sensitivity Analysis at Week 12
Exploratory Endpoints		
Change of following variables from baseline at Week 12: Thyroid Function Test : TSH, T3, and T4 Serum Parameters : zinc, insulin, adiponectin, C-peptide, leptin, and glucagon Urine Parameters : zinc, glucose, microalbumin, and copper TAFGC BMI	1. EAS: Summary statistics by visit using observed data 2. EAS: ANOVA model and Dunnett's test, and paired t-test	1. Per Protocol Set : Same as primary summary and analysis method at Week 12

### 10.5.1 Primary Efficacy Analyses

- The change of HbA1c level from baseline at Week 12 will be summarized with mean, standard deviation, median, 25th & 75th percentiles, minimum, and maximum, overall and by each of the four groups, separately. To identify statistically significant difference in the change of HbA1c level from baseline at Week 12 between the four groups, one-way ANOVA will be performed. The tests between the experimental groups and the control group will be performed using Dunnett's test. If the change variables are markedly non-normally distributed then Kruskal-Wallis test and Wilcoxon rank-sum test will be used respectively. Specifically, all three experimental groups will be compared to the control group on the change: Dose A vs. D, B vs. D, and C vs. D. Also, to identify statistical significant difference between baseline and Week 12, one-sample t-test (paired t-test) or Wilcoxon signed-rank test will be performed within each of the four groups.
- The change of BW from baseline at Week 12 will be summarized with mean, standard deviation, median, 25th & 75th percentiles, minimum, and maximum, overall and by each of the four groups, separately. To identify statistically significant difference in the change of BW from baseline at Week 12 between the four groups, one-way ANOVA will be performed. The tests between the experimental groups and the control group will be performed using Dunnett's test. If the change variables are markedly non-normally distributed then Kruskal-Wallis test and Wilcoxon rank-sum test will be used respectively. Specifically, all three experimental groups will be compared to the control group on the change: Dose A vs. D, B vs. D, and C vs. D. Also, to identify statistical significant difference between baseline and Week 12, one-sample t-test (paired t-test) or Wilcoxon signed-rank test will be performed within each of the four groups.
- Sensitivity analysis described below will be performed for the primary endpoints at Week 12:
  1. Summary statistics and ANOVA model for continuous endpoints using imputed data by LOCF, EAS.
  2. Primary summary and analysis method based on Per Protocol Set.

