#### 8.1.3 Primary Efficacy Analyses

The change from baseline to Week 12 in HbA1c will be compared for the experimental groups versus the control group using analysis of variance (ANOVA) methods if the change is approximately normally distributed. If the change is markedly non-normally distributed then Wilcoxon rank sum tests will be used. Specifically, all three experimental groups will be compared to the control group on the change: Dose A vs. D, B vs. D, and C vs. D.

The change from baseline to Week 12 in BW will be compared for the experimental groups versus the control group using ANOVA methods if the change is approximately normally distributed. If the change is markedly non-normally distributed then Wilcoxon rank sum tests will be used.

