### 6. DEFINITIONS

- **Baseline** is defined as the last non-missing measurement taken on Week 0.
- **Study day 1** is defined as the first IP dose date. For subjects who are randomized but not dosed after randomization, the study day 1 is defined as the date of randomization.
- **Study day** is defined as the number of days from study day 1.

Before study day 1: study day = (date of interest – date of study day 1)

On or after study day 1: study day = (date of interest – date of study day 1) + 1

Therefore, the day prior to study day 1 is -1.

- **Study drug exposure day** is defined as the number of days that subjects were on the study drug.
- **Age (years)** is calculated as follows, and is rounded down to an integer.

$$Age = \frac{Date\ of\ Informed\ Consent - Date\ of\ birth}{365.25}$$

- **Diabetes disease period (years)** is calculated as follows, and is rounded down to an integer.

$$Diabetes\ disease\ period = \frac{Date\ of\ Screening - Date\ of\ diagnosis^*}{365.25}$$

\*If the month and day of date of diagnosis are unknown, it will be converted into January, first day.

- **OGTT** of secondary endpoint is used glucose value at 2 hour after glucose intake.
- **TAFGC** is calculated as follows:

$$TAFGC = \frac{\sum_n [Glucose\ value\ at\ (n)\ hour\ in\ OGTT - Glucose\ value\ at\ 0\ hour\ in\ OGTT]}{6},$$

where  $n = 0.5, 1.0, 1.5, 2.0, 2.5, \text{ and } 3$

- **BMI (kg/m^2)** is calculated as follows:

$$BMI = \frac{Body\ Weight\ (kg)}{Height\ (m) \times Height\ (m)}$$

- **Compliance (%)** is calculated as follows:

$$compliance = \frac{Number\ of\ capsules\ taken}{Number\ of\ capsules\ should\ be\ taken\ in\ principle^*} \times 100$$

\*By visit:  $Date\ of\ Visit(n) - Date\ of\ Visit(n - 1)$ , where  $n=3, 4, 5, 6, 7, \text{ and } 8$

Overall:  $\sum_n (Date\ of\ Visit(n) - Date\ of\ Visit(n - 1))$ , where  $n=3, 4, 5, 6, 7, \text{ and } 8$

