## 7.2 Efficacy Analysis Set

The Efficacy Analysis Set (EAS) will be used to carry out the efficacy analyses of efficacy endpoints, which is a subset of the FAS consisting of subjects who received at least one dose of study medication and who had baseline and any post-baseline efficacy data. Subjects will be analyzed according to their randomized treatment, regardless of the treatment received. Analyses for efficacy endpoints will utilize this analysis set.

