### 9.3.2 Missing Baseline Evaluation

Missing baseline will not be imputed.

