## 12. ADJUSTED STATISTICAL ANALYSIS METHOD

Not applicable.

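### No planned analysis of HbA1c or weight change adjusts for baseline; for HbA1c this can lose precision and leave part of a chance baseline gap in the estimate

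*SAP*

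**What the plan says.** Protocol 8.1.3 has the change to Week 12 "compared for the experimental groups versus the control group using analysis of variance (ANOVA) methods". SAP 10.5.1 makes this a one-way model: to look for a difference "in the change of HbA1c level from baseline at Week 12 between the four groups, one-way ANOVA will be performed", followed by Dunnett's test of A, B and C against D. Body weight is treated identically. If the change is markedly non-normal, Kruskal-Wallis and Wilcoxon rank-sum tests replace these, also without adjustment.

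The two named sensitivity analyses keep the same model. One is "Summary statistics and ANOVA model for continuous endpoints using imputed data by LOCF, EAS". The other, in the Per Protocol Set, is "Same as primary summary and analysis method at Week 12" (table in SAP 10.5). The optional outlier and post-hoc analyses (SAP 9.5, 10.8 and 10.9) specify no model.

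The heading of SAP 4 mentions covariates, but its subsections name none. SAP 12, on adjusted methods, reads "Not applicable". Baseline efficacy values are tabulated by arm (SAP 10.4.4) and not otherwise used.

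The covariate is already collected. Baseline "is defined as the last non-missing measurement taken on Week 0" (SAP 6). The Efficacy Analysis Set is limited to randomized subjects "who received at least one dose of study medication and who had baseline and any post-baseline efficacy data" (SAP 7.2). SAP 9.3.2 adds: "Missing baseline will not be imputed".

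**The concern.** A change score subtracts baseline with a fixed slope of 1. If the true slope of Week 12 on Week 0 is not 1, two things follow. Residual variance is larger than it need be, and part of any chance difference in baseline between two arms stays in the estimated effect. With a slope below 1, the arm that starts higher by chance shows the larger fall.

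This matters more here than in a large trial. There are 16 subjects per arm and no stratification is described. All three contrasts share one placebo arm, so a chance gap in placebo moves all three the same way. The primary objective is dose-dependent efficacy, and separate gaps in the dose arms could imitate or hide a dose order. Tabulating baseline shows such a gap but does not correct for it.

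**Working it through.** **Inputs from the documents.** Four arms of 16, 64 in all (SAP 3.4.1), hence 60 error degrees of freedom. HbA1c of 7.5 to 10.0% at Screening (SAP 3.2.1). The sample size has no power basis (SAP 3.3) and no SD, correlation or effect size is given, so there is no planned figure to reproduce.

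**Assumed inputs.** s0 and s1 are the SDs at Week 0 and Week 12, and ρ is their correlation. The ranges are shown below.

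**Step 1, precision.** The ANCOVA/change-score variance ratio before cost is s1²(1−ρ²) / (s0² + s1² − 2ρ·s0·s1), which is (1+ρ)/2 when the SDs are equal. Estimating the slope multiplies it by 1 + 1/(60−2) = 1.017. The equivalent number per arm is 16 / (ratio after cost).

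Example, equal SDs, ρ = 0.6: (1+0.6)/2 = 0.80; 0.80 × 1.017 = 0.81; about 19.7 per arm.

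Example, SDs 0.7 and 1.0, ρ = 0.7: 0.51 / (0.49 + 1 − 0.98) = 1.000; after cost 1.02.

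| Case | ρ | Before cost | After cost | Equivalent n per arm |
|---|---|---|---|---|
| HbA1c, equal SDs | 0.4 | 0.70 | 0.71 | 22.5 |
| | 0.6 | 0.80 | 0.81 | 19.7 |
| | 0.8 | 0.90 | 0.92 | 17.5 |
| HbA1c, SDs 0.7 / 1.0 | 0.5 | 0.949 | 0.97 | 16.6 |
| | 0.6 | 0.985 | 1.00 | 16.0 |
| | 0.7 | 1.000 | 1.02 | 15.7 |
| | 0.8 | 0.973 | 0.99 | 16.2 |
| Weight, equal SDs | 0.95 | 0.975 | 0.99 | 16.1 |
| | 0.98 | 0.990 | 1.01 | 15.9 |
| | 0.99 | 0.995 | 1.01 | 15.8 |

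For HbA1c with equal SDs, confidence intervals narrow by 16%, 10% and 4% (square root of the ratio). Simulation of four arms of 16, with 20,000 trials per case, agreed: 0.72 / 0.82 / 0.92 for equal SDs; 0.97 / 1.02 / 0.99 at ρ 0.5 / 0.7 / 0.8 for SDs 0.7 and 1.0; 0.99 / 1.01 for weight at ρ 0.95 / 0.99.

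**Step 2, chance baseline gap.** The SE of a two-arm gap is s0·√(2/16). The slope of change on baseline is ρ·s1/s0 − 1, and the shift in the unadjusted effect is that slope times the gap. Signs below are for the arm with the higher baseline.

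- HbA1c, equal SDs of 0.722 (the SD of a uniform distribution on 7.5 to 10.0, 2.5/√12; an assumption, since the limit applies at Screening and not at Week 0). SE = 0.722 × 0.354 = 0.255; 1.96 SE = 0.50 points. Shift: −0.30 / −0.20 / −0.10 points at ρ 0.4 / 0.6 / 0.8.
- HbA1c, SDs 0.7 and 1.0. SE = 0.247; 1.96 SE = 0.49 points. Shift: −0.14 / −0.07 / 0.00 / +0.07 at ρ 0.5 / 0.6 / 0.7 / 0.8.
- Weight, SD 15 to 20 kg, ρ 0.95 to 0.99. SE = 5.3 to 7.1 kg. Size of shift: 0.05 to 0.35 kg for a 1-SE gap, about 0.10 to 0.69 kg for a 1.96-SE gap.

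For scale, Protocol 1.1 cites a 12-week HbA1c fall of 0.39 to 0.56% for a DPP-4 inhibitor. A shift of 0.20 is 0.20/0.56 = 36% to 0.20/0.39 = 51% of that. In simulation, at least one of the three baseline gaps exceeded 1.96 SE in about 12% of trials. The median largest gap was about 1.18 SE, or 1.18 × 0.255 = 0.30 points.

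**Step 3, restricted entry.** Simulations with Screening HbA1c truncated to 7.5 to 10.0% gave these variance ratios:

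- No mean reversion: 0.99 to 1.02 (population SD 1.0 to 1.5, measurement error 0.15 to 0.25, drift SD 0.4 to 0.8).
- 20% reversion, same inputs: 0.86 to 0.98.
- A wider range of assumed reversion: 0.67 to 1.02.

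**The case against.** The strongest reply is that this is an efficiency preference in a small exploratory trial that claims no power. The unadjusted ANOVA is valid, keeps its type I error, and is stated consistently in both documents. One of the two co-primary endpoints gains nothing. The larger HbA1c gains need equal SDs and a correlation of 0.4 to 0.6, while the entry limit narrows baseline more than Week 12 and so tends to bring the gain close to zero unless HbA1c reverts to the mean. All of that stands. It limits the size of the benefit and rules out calling the plan wrong. It does not show that the gain is absent: once reversion is allowed for, the same restricted-entry setting gives ratios well below 1.

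Three smaller points also stand. The primary analysis uses observed data (SAP 9.3.3), so the cost is slightly above 2% if subjects drop out: at 12 per arm it is 1/(44−2) = 2.4%. Removing the expected effect of a gap requires a linear slope common to the arms. If the rank-test fallback is triggered, the analysis is again unadjusted. None of these outweighs the balance of a cost near 2% against a possible gain worth several subjects per arm.

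**Conclusion.** The concern holds. No primary, fallback or named sensitivity analysis of HbA1c or weight adjusts for baseline. For HbA1c the consequence runs from no loss (variance ratio 1.02) to a material one (0.71 in the tabulated cases, 0.67 in the most favourable simulation). A 1.96-SE baseline gap could move the estimate by up to 0.30 points under equal SDs, and by less, in either direction, under SDs of 0.7 and 1.0. For weight there is no material effect on precision. That no covariate is planned is certain. The sizes depend entirely on assumed SDs, correlations and reversion. When the slope is unknown, estimating it is the safer choice than fixing it at 1, so the change should be made, although the planned analysis would be valid without it.

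**What to change.** Before unblinding, make the primary model in SAP 10.5.1 an ANCOVA: Week 12 change on treatment plus that endpoint's own Week 0 value. Compare the adjusted means of A, B and C with D using Dunnett's adjustment, and report adjusted differences with 95% CIs. Carry the model into the LOCF and Per Protocol analyses, and keep the unadjusted one-way ANOVA as a further sensitivity analysis. The rank-test fallback can stand, but is best triggered by the model residuals. Name the covariate in SAP 4, revise SAP 10.5 and 12, and record the departure from Protocol 8.1.3 in SAP 13. The reason is HbA1c; using the same model for weight and the other continuous endpoints would be for consistency only.

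The cost is SAP wording and one model term. It uses 1 of 60 error degrees of freedom (the two-sided 5% Dunnett critical value is about 2.41 either way) and at worst about 2% of variance with full follow-up. It needs no new data and loses no subject, because a change score already requires the Week 0 value. Fixing the covariate before unblinding avoids the appearance of a choice driven by the data.
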